The lag for the VA Vital Status files is only about 6-12 months so this file will allow us to have 1 year additional follow-up for total mortality than we will have

for disease-specific mortality. Therefore total mortality will be obtained from the VA Vital Status files, which combine death dates from all sources currently available to VA researchers, including the Medical SAS Inpatient Datasets, the Veterans Benefits Administration's (VBA) Beneficiary Identification and Resource Locator System (BIRLS), the Medicare Vital Status file, and the Social Security Administration (SSA) death file. A review of major US mortality databases found that these sources are quite accurate for mortality (Dominitz, 2001).

Measuring Endpoints:

The following endpoints will always be adjudicated: 1) non-fatal cardiac-related admissions to non-VA hospitals in those which hospital discharge data are not available (those <65 years old who report such events on the survey), and 2) all amputations (to determine if the amputation was ischemic [a primary endpoint], non-ischemic gangrene [a secondary endpoint] or traumatic [neither a primary nor secondary endpoint]). Death and hospital discharge records will be relied upon for other endpoints at VA facilities (using central VA data) and CMS data will be used to capture events at non-VA facilities for over 65. Past experience has shown that discharge diagnosis for MI and stroke are highly accurate that the patient has truly had these events, and therefore such designations are generally relied upon in observational studies. This of course is not done in experimental studies in which investigators in the field may bias endpoint determination, a concern that does not exist in this observational follow-up study with central data collection.

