Although eye disease is not a component of the VADT-FS's primary outcome, it is a very important component of a secondary outcome (major microvascular events). As above, the discontinuation of standard routine physical examinations makes continuation of visual acuity and retinopathy stage determinations problematic. Fortunately, there is now available a patient self-report visual function tool that has been developed with NIH support. (Mangione, 2001; Naeim, 2006; Raphael, 2006) This National Eye Institute Visual Function Questionnaire includes a validated single question for general visual function, and those reporting poor or worse function on this item have been validated to have substantial functional impairment impacting their quality of life (Mangione, 2001 and personal communication with [name] in January 2007). Although caution is always advised when including a new measure during the course of a longitudinal study, we feel that the adoption of this validated item measuring marked visual impairment is preferable to dropping measures of visual function altogether. Patients with reported visual problems will be informed that they can complete their surveys either using the assistance of their designated surrogate or by telephone, whichever they prefer.

Primary study end-point:

Major CV events (non-fatal MI resulting in hospitalization, non-fatal stroke, new CHF, amputation for ischemic diabetic gangrene, or CV-related death).

The proposed primary end-point of the VADT-FS is slightly more restrictive than the primary end-point of the VADT [excluding some CV procedures and subclinical AMI's based upon ECG changes alone] because the increased statistical power of the VADT-FS will allow greater focus on major clinical outcomes and avoid outcomes that are more difficult to discern (e.g., worsening of symptoms) or are more discretionary (e.g., cardiac

procedures).

Major secondary end-points:

1. CV mortality
2. Major microvascular complications (end-stage renal disease, or amputation for non-traumatic, non-ischemic diabetic gangrene).
3. Health-related quality of life (as measured by the modified DCCT tool on a 0-100 point scale)
4. Total mortality

Update

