We have revised the composition of our adjudication team, which now includes 2 hospitalist physicians and a cardiologist. This change was made because fewer neurological and cardiac outcomes are being adjudicated in the VADT-F than in the original VADT, making hospitalists an excellent choice for the adjudication committee.

We propose adding a fifth secondary end-point: Major microvascular or macrovascular complication (*end-stage renal disease, amputation for either ischemic or non-ischemic gangrene, CV-related death, or nonfatal MI, stroke, or new CHF*).” *This secondary endpoint was added for two reasons. First, this is a composite of all major micro- and macro-vascular endpoints and therefore has better statistical power and great clinical importance. Second, this also helps when making direct comparisons with other trials.* The addition of this outcome was recommended by the Executive Committee, who is blinded to all outcome data in the VADT-FS and therefore this recommendation was made without any knowledge of results to date. (Note: New CHF will be determined by a subject having either: 1. A hospital stay with a primary discharge diagnosis of CHF, or 2. chart review finding an ejection fraction on echocardiogram estimated as being below 40%.)

Healthcare Utilization & Cost Data

Initial collection of recent data on healthcare utilization and costs incurs a fairly modest cost, but such data collection can be much more expensive when done retrospectively. Therefore, we will obtain permission to collect this data, but no initial funds are being requested for data cleaning and analysis. (Barnett, 2003; Wagner, 2003; Phibbs, 2003) Funds for analysis of data on total direct healthcare costs will be requested in a separate proposal, and funds for formal cost-effectiveness analysis will only be requested if the intervention is eventually shown to produce statistically significant benefit. This is similar to incurring the small costs of storing extra sera to be analyzed as indicated. We estimate that the cost to obtain and store this data at the same time that we obtain information on potential outcomes to be < \$10,000 a year.

Update

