Given the current rate of overall events observed in the VADT, Table 2. below shows the expected statistical power that the VADT-FS will have for its primary and secondary outcome measures. As a continuous measure, statistical power for health related quality of life will be even better.

Table 2. Power Calculations for VADT-FS*

	Overall Study Event Rate	At 6 year Follow-up (end of VADT)	At 10 year Follow-up†	At 15 year Follow-up†
	(events per 1000 person-years)	Statistical Power to detect a Hazards Ratio of 0.8*		
CV events (Primary Outcome)‡	51.9	0.93	0.98	0.99
CV Mortality	5.5	0.00	0.08	0.31
Micro-vascular events§	31.4	0.00	0.35	0.71
Total Mortality	13.7	0.00	0.14	0.43

* All power calculations are for 2-tailed testing and assume $\alpha=0.05$.

† Estimates assume 85% retention of study subjects from the VADT and attrition due to mortality.

‡ Major CV events include: non-fatal heart attack, non-fatal stroke, new CHF, amputation for ischemic diabetic gangrene, or CV death).

§ Microvascular events include: end-stage renal disease, irreversible severe visual impairment [i.e., excludes visual acuity problems correctable by cataract surgery], or amputation for ischemic diabetic gangrene).

Update

Given the achieved sample size of the VADT-FS Main Cohort (N= 1031 as of July 31, 2011), the updated power at 15-year follow-up is now 86.3%, which is still excellent. Based on additional information, the power for detecting effects for CV and total mortality are better than what we previously thought but are still under 30%. Although power for mortality is still poor, these results will be useful for inclusion in future meta-analyses.

Objective #1: To determine the long term effects of intensive glycemic control in type 2 diabetes on major cardiovascular complications (primary outcome).

The primary outcome measure is the time to the first of any of the following events: nonfatal heart attack, nonfatal stroke, new congestive heart failure, amputation for ischemic gangrene, or cardiovascular death. The assessment of endpoints comparing the

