We have added a composite measure “Major Microvascular & Macrovascular Events, which is simply an aggregate of the primary outcome with the secondary outcome for microvascular outcomes. Statistical analyses for secondary outcomes will be identical to those used for the primary outcome, with the exception of health related quality of life. Since health related quality of life is a continuous measure, survival analysis will not be appropriate for this secondary outcome. The Student t-test will be used to evaluate for differences in mean quality-of-life scores in the two treatment arms, with use of robust methods if there is evidence that variance estimates vary between the two groups. It is well known that if there is a substantial difference in survival between intervention groups, health related

quality of life results can be misleading unless the survival differences are accounted for. Therefore, if there are substantial differences in survival between treatment groups, an alternative analysis accounting for missing data due to mortality using a Bayesian imputation approach (Revicki, 2001), which will be done by Ann Arbor according to their IRB permission on mortality data collection on all VADT population except the terminated. Again, since substantive differences in baseline attributes did not occur, we do not feel that controlling for potential confounders using ordinary least squares regression is necessary. For the quality of measure, we will deal with confounding due to systematic mortality differentials between treatment arms by using selection models, as recommended in *Assessing Quality of Life in Clinical Trials: Methods and Practice* (eds. Fayer P, Hays R, April 2005.)

Update: (Early Analysis)

The major protocol amendment for the VADT-F was that a mid-point analysis would be conducted and reported, which was made and published as planned. We now plan for an early analysis to take place shortly before data is fully completed with adjudicated outcomes and locked. There is to prepare to submit an important presentation in time to take place at the American Diabetes Association (ADA) 2018 which is planned to be made in conjunction with publication of the corresponding manuscript. Below we provide the full justification for this analysis.

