In addition to examining interaction effects (factors that modify the intervention's effect), we will examine factors that are hypothesized to mediate the interaction effect. Whereas interaction effects are part of the experimental analysis (examining baseline [pre-randomization] subject attributes that identify individuals or groups who will benefit more or less than average), examination of potential mediating factors are observational analyses (examining factors post-treatment but prior to the occurrence of an outcome trying to better understand the treatment's mechanism(s) of action).(Hayward, 2006) There are two principle hypothesized mechanisms of action for why improved metabolic control may reduce CV events: 1) direct effects of hyper-glycemia on blood vessels and atherosclerotic disease, and 2) decreasing the prevalence of diabetic nephropathy and proteinuria (microvascular complications known to increase with hyperglycemia), which in turn reduces risk of CV events. We will examine these two factors following the methods used in the DCCT/EDIC.(Nathan, 2005) The variable examining direct hyperglycemic effects will be based upon the log of cumulative average A1c (previous observational analyses have consistently reported a log-linear association between A1c and adverse outcomes), which will be updated annually for all subjects who have not yet reached the endpoint. Markers for diabetic nephropathy previously reported to be associated with CV risk, include presence of proteinuria and estimated GFR. In addition to the log of cumulative average A1c, proteinuria and GFR, this analysis will control for a subject's other CV risk factors. (Fleiss, 1986) Cox proportional hazards regression will be used for these analyses, except for the visual impairment outcome which was not collected during the original VADT. Since time of the event is not available, logistic regression will be used for this outcome.

Missing Data

In longitudinal studies relying on survey or tests ordered in routine clinical practice, problems of missing data will almost always increase. Fortunately, our primary outcome and three of our four secondary outcomes do not rely on these data sources. However, our

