analysis of health related quality of life will be limited to those subjects who have answered the survey. For those analyses of interaction effects and potential mechanisms of action, outlined above, standard multiple imputation techniques will be utilized so as to prevent diminished sample size and potential response bias due to dropping subjects with missing data on covariates. (King, 2001; Revicki, 2001; Carroll, 1995) Imputed values for a given covariate will be informed by an individual's values for all other observed covariates to be used in the regression model, as well as temporal trends in the study population and previous values for that covariate in the individual. Multiple imputation is preferable in such instances, since it accounts for the degree of precision in imputed values and therefore provides better variance estimates for all regression coefficients. (King, 2001; Clayton, 1991; Carroll, 1995; Gatsonis, 1995; Oppenheimer, 1999)

Updates

There are no anticipated changes in the planned analyses, other than the addition of the new composite secondary endpoint, "Major Microvascular & Macrovascular Events" (see Endpoints Section) except severe visual impairment, which will be analyzed independently from other outcomes using only data collected through self-administered survey questionnaire during this follow-up period since 2009.

Study Significance.

The proposed extension of the VADT Follow-up Study (VADT-FS) would capitalize on a unique opportunity to examine factors that are associated with long-term complications and mortality for people with one of the most important conditions in modern medicine, a disease that will continue to grow dramatically if current epidemiological trends continue. Given the results of the UKPDS Follow-up Study and the DCCT-EDIC study, the objectives of the VADT-FS are important to answer in order to better assess possible multiplicative temporal effects and to obtain adequate statistical power to assess mortality benefits directly. It will also provide an opportunity to assess the long-term impact of tight glycemic control on vision and renal insufficiency when tight blood pressure control is achieved, a question unanswered by previous studies.

References:

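### Table 2's microvascular power (0.71 at 15 years) belongs to a composite that shares only end-stage renal disease with the listed secondary endpoint, and it was not restated for the achieved 1,031

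*Combined protocol and SAP*

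**What the plan says.** **The power table.** Table 2 (Analysis Plan, Statistical power) is for a hazard ratio of 0.8 with a two-sided 0.05 test, at event rates said to have been observed in the VADT. The microvascular row shows 31.4 per 1,000 person-years and power 0.00, 0.35 and 0.71 at 6, 10 and 15 years. Its footnote counts ESRD, "irreversible severe visual impairment [i.e., excludes visual acuity problems correctable by cataract surgery], or amputation for ischemic diabetic gangrene". On numbers, the table notes: "Estimates assume 85% retention of study subjects from the VADT and attrition due to mortality".

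**The endpoint list.** Under Major secondary end-points, item 2 is "Major microvascular complications (end-stage renal disease, or amputation for non-traumatic, non-ischemic diabetic gangrene".

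**Related text.**
- Measuring Endpoints sorts amputations as "ischemic [a primary endpoint], non-ischemic gangrene [a secondary endpoint] or traumatic [neither a primary nor secondary endpoint".
- The Update after the endpoint list defines the fifth secondary outcome as "end-stage renal disease, amputation for either ischemic or non-ischemic gangrene, CV-related death, or nonfatal MI, stroke, or new CHF". The Objective #2 Update describes that outcome as one "which is simply an aggregate of the primary outcome with the secondary outcome for microvascular outcomes".
- The Updates under Missing Data make an exception for vision: "except severe visual impairment, which will be analyzed independently from other outcomes using only data collected through self-administered survey questionnaire".
- Pointing the other way, the Measuring Endpoints narrative still calls eye disease a component of the microvascular outcome. The main Objective #2 text prescribes logistic regression for microvascular complications because visual impairment comes from the survey.

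**The power update.** For the Main Cohort of 1,031, the Update to Statistical power gives 86.3% at 15 years (endpoint unnamed, evidently the primary) and under 30% for CV and total mortality. It gives nothing for microvascular events.

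**The concern.** A power figure is meaningful only for the endpoint, event rate and sample size behind it. Here the endpoint behind 31.4 and 0.71 differs from the listed one in two of its three components: it includes vision, and it counts the type of amputation that the plan assigns to the primary outcome. The sample size is also superseded.

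A reader of Table 2 would take 0.71 as the chance of detecting a hazard ratio of 0.8 on the second-listed secondary outcome, and could read a null result as stronger evidence of no effect than it is. The Data Monitoring Committee is charged with checking whether the power assumptions are met, and it cannot do so for an outcome whose stated power describes another composite. The same conflict leaves two tests on the page for one endpoint, logistic regression and log-rank.

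**Working it through.** **1. Which definition governs**

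| Component | Table 2 footnote | Endpoint list, item 2 |
|---|---|---|
| ESRD | yes | yes |
| Severe visual impairment | yes | no |
| Amputation, ischemic gangrene | yes | no (primary endpoint) |
| Amputation, non-ischemic gangrene | no | yes |

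The fifth secondary outcome is described as the primary plus the microvascular outcome. Removing the primary components (MI, stroke, new CHF, ischemic amputation, CV death) from its list leaves ESRD and non-ischemic amputation, which is item 2 exactly, with no visual item. The amputation rule in Measuring Endpoints and the separate analysis of vision agree with this.

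**2. Source of the rate**

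The rates are said to come from the VADT, but Evaluation of Mechanisms of Action uses Cox regression "except for the visual impairment outcome which was not collected during the original VADT". The visual part of 31.4 therefore cannot be the survey measure used in follow-up.

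**3. Reproducing 0.71**

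Inputs from the documents: HR 0.8, two-sided 0.05, λ = 0.0314 per year, N = 0.85 × 1,791 = 1,522. My assumptions: 1:1 allocation, exponential times, λ as the pooled rate, and competing death at μ = 0.0137 per year (Table 2's total mortality rate).

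- Expected events: D = N × λ/(λ+μ) × [1 − exp(−(λ+μ)T)]
- Power (Schoenfeld): Φ(½√D × |ln 0.8| − 1.96), with |ln 0.8| = 0.2231

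At T = 15: D = 1,522 × (0.0314/0.0451) × [1 − exp(−0.6765)] = 1,522 × 0.6962 × 0.4916 = 521. Power = Φ(11.41 × 0.2231 − 1.96) = Φ(0.59) = 0.72, against the stated 0.71. The 15-year figure is reproduced, but for the footnote's composite and at 85% retention.

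**4. Achieved numbers, rate kept at 31.4**

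- 1,791 to year 6, then 1,031/1,791 = 57.6% of those still at risk. Years 0–6: 1,791 × 0.6962 × [1 − exp(−0.2706)] = 296. Years 6–15: 1,031 × exp(−0.2706) × 0.6962 × [1 − exp(−0.4059)] = 183. D = 478 before rounding the parts; power 0.68. If all 1,031 are taken as alive at year 6, power is about 0.70.
- 1,031 throughout: D = 1,031 × 0.6962 × 0.4916 = 353; power 0.55.

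Which scenario fits the plan's own update? For the primary rate of 51.9, the first gives 0.84 (μ = 0.0137) to 0.87 (μ = 0), against the stated 86.3%; 1,031 throughout gives 0.71 to 0.75. The update is thus consistent with counting VADT-period events of all 1,791.

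**5. The listed endpoint**

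The documents give no rate for it. 15-year power at assumed rates per 1,000 person-years:

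| Assumed rate | 1,522 throughout | 1,791 to year 6, then 1,031 | 1,031 throughout |
|---|---|---|---|
| 5 | 0.20 (D = 100) | 0.18 (89) | 0.15 (67) |
| 10 | 0.34 (192) | 0.31 (173) | 0.25 (130) |
| 15 | 0.46 (278) | 0.42 (251) | 0.33 (188) |
| 20 | 0.56 (358) | 0.52 (325) | 0.41 (243) |

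Power 0.71 needs D = 4 × (1.960 + 0.553)² / 0.2231² = 507. The listed endpoint would then need a rate of about 30.4, 33.8 or 51.4 in the three scenarios.

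**6. Limit of the model**

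With 1,522, the same formulas give 0.42 and 0.59 at 6 and 10 years for this row (stated 0.00 and 0.35), and 0.60, 0.77 and 0.87 for the primary row (stated 0.93, 0.98 and 0.99). An unconditional two-sided 0.05 test cannot have power 0.00. The method behind Table 2 is therefore not established, and the agreement at 15 years may be partly chance.

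**The case against.** **The footnote may contain a slip.** Table 2's own note on the primary outcome also claims ischemic amputation, so a dropped prefix non- is possible, with 31.4 counted on the right amputations. The documents cannot settle that. Even so, the row would still include vision, which item 2 does not. If instead vision is kept, as the Measuring Endpoints narrative and the main Objective #2 text suggest, two components are shared but the amputation type is still the opposite one. Neither repair alone makes the row match the list.

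**The change of visual measure is disclosed.** The plan says that routine eye examinations ended with the VADT and that the questionnaire item is new. VADT examinations are a plausible source for the visual part of 31.4. This stands, and it means that part does not carry over to follow-up.

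**The test is largely settled by the Updates.** The Objective #2 Update exempts only quality of life from the primary's method, and the Missing Data Updates separate vision. This stands: the logistic regression sentence is leftover wording, and correcting it is tidying.

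**The size of the loss is uncertain.** On the scenario that fits 86.3%, the change in numbers alone costs about four points (0.72 to 0.68). The rest depends on assumed rates and on a model that does not reproduce the other cells checked. This stands, and no single replacement figure should be quoted.

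**Little depends on the cell.** The cohort is fixed, no sample size or alpha rests on this row, and a null result should be read from its confidence interval. This limits the consequence, but it does not make the stated power apply to the endpoint.

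**Conclusion.** The concern holds. The arithmetic of 0.71 is not the fault: the figure is approximately reproduced for the composite and retention it assumes. That composite shares only ESRD with the listed endpoint, and the retention was not achieved, so the documents give no power for major microvascular complications as they will be tested.

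The mismatch and the missing update are certain from the text, taking the endpoint list as governing. The numerical loss is not. At the unchanged rate, power is about 0.68 with 1,791 to year 6 then 1,031, and 0.55 if only the 1,031 count throughout. At assumed rates of 5 to 20 per 1,000 person-years it is 0.15 to 0.56 across all three scenarios. Removing vision and ischemic amputation while adding non-ischemic amputation probably lowers the rate, but no component rates are given. These figures rest on exponential times, mortality of 13.7 per 1,000 person-years and the Schoenfeld formula, which may not be Table 2's method.

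**What to change.** 1. Put the item 2 definition (ESRD, or amputation for non-traumatic, non-ischemic gangrene) in the Table 2 footnote and in Objective #2, and reconcile the Measuring Endpoints sentence that calls eye disease a component.
2. Recount the rate of that endpoint from existing VADT data. Replace 31.4 and 0.71 with that rate and the power at the achieved numbers, naming the method and stating whether VADT-period events of subjects who did not consent to follow-up are counted.
3. Amend the main Objective #2 text so that major microvascular complications are compared by log-rank, as its Update implies. Take severe visual impairment out of the composite and analyse it separately by logistic regression on the survey data.

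The cost is wording in three places and one recount of existing events. The stated power will probably fall. No new data are needed, and neither the cohort nor the primary analysis changes. It should be done before the planned early analysis.

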original study glycemic treatment arms will be analyzed as per original intent-to treat using methods identical to the current VADT study. Life table methods and the log-rank test will be used to compare complication-free survival between the two treatment groups. (Halpern, 1987) Preliminary analyses suggest that the treatment groups were quite similar on important factors at baseline, so we do not anticipate needing to use Cox proportional hazards regression to control for baseline confounding. (Halpern, 1987) However, Cox proportional hazards regression methods will be used to perform a time-dependent covariate survival analysis of the primary outcome. This analysis will adjust for risk factors post intervention such as A1 c, weight, BMI, SPB, DBP, cholesterol, HDL, LDL, use as time dependent covariates. The progress report will include these post-intervention risk factors summarized over time as available through database search.

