Objective #2. To determine the long term effects of intensive glycemic control in type 2 diabetes on four secondary outcomes: a) cardiovascular mortality, b) major microvascular complications, c) health-related quality of life, d) total mortality, and e) major microvascular or macrovascular (end-stage renal disease, amputation for either ischemic or non-ischemic gangrene, CV-related death, or nonfatal MI, stroke, or new CHF). Statistical analyses for secondary outcomes will be identical to those used for the primary outcome, with the exception of microvascular complications and health related quality of life. Since one of the microvascular complications, severe visual impairment, is from the annual survey, survival analysis is not appropriate for the inaccuracy of the time of the record but logistic regression analysis. Since health related quality of life is a continuous measure, survival analysis will not be appropriate for this secondary outcome. The Student t-test will be used to evaluate for differences in mean quality-of-life scores in the two treatment arms, with use of robust methods if there is evidence that variance estimates vary between the two groups. It is well known that if there is a substantial difference in survival between intervention groups, health related quality of life results can be misleading unless the survival differences are accounted for. Therefore, if there are substantial differences in survival between treatment groups, an alternative analysis accounting for missing data due to mortality is a Bayesian imputation approach. (Revicki, 2001) Again, since substantive differences in baseline attributes did not occur, we do not feel that controlling for potential confounders using ordinary least squares regression is necessary.

Update

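### If non-CV death is censored, the life-table curves overstate each arm's 15-year risk of the primary endpoint; state the rule and show cumulative incidence

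*Combined protocol and SAP*

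**What the plan says.** Under Analysis Plan, Objective #1, the primary outcome is time to the first of "nonfatal heart attack, nonfatal stroke, new congestive heart failure, amputation for ischemic gangrene, or cardiovascular death". The comparison of the original arms is by intention to treat, with methods said to be the same as in the parent trial: "Life table methods and the log-rank test will be used to compare complication-free survival between the two treatment groups".

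Under Objective #2 the plan says "Statistical analyses for secondary outcomes will be identical to those used for the primary outcome". In the main text that sentence goes on to exempt both microvascular complications (logistic regression) and quality of life. The Update that follows exempts only quality of life. Read with the Update, CV mortality, the microvascular endpoint and the added micro- or macrovascular composite are all analysed by life table and log-rank.

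No section states how a death outside the endpoint is treated, and none mentions cumulative incidence or another competing-risk method. The footnote to Table 2 treats mortality as attrition, which fits censoring but does not prescribe it. Death is handled analytically only for quality of life, where the plan accepts that survival differences can mislead and proposes imputation and selection models. Measuring Endpoints classes cause of death as cardiovascular, neoplasm, other or undetermined.

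**The concern.** A life-table estimate that censors non-CV deaths treats those patients as still able to have a first CV event. One minus that estimate is the risk in a hypothetical population where nobody dies of anything else. It is not the proportion of patients who have the event, although a curve labelled complication-free survival will be read that way.

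The gap grows with follow-up and with the competing death rate. Here the horizon is about 15 years in a cohort with mean entry age 60.5 (Table 1), and the rates in Table 2 come from the trial phase, when patients were younger. The Statistical power section justifies the 20% target partly by weighing benefit against the risk and burden of intensive control. A reader making that judgement from the curves needs the risk that patients actually face.

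**Working it through.** **Inputs.** All are from Table 2 unless noted, per 1000 person-years.
- Primary events: "CV events (Primary Outcome)‡ 51.9 0.93 0.98 0.99", so 51.9.
- Deaths: "CV Mortality 5.5" and "Total Mortality 13.7", so non-CV death = 13.7 - 5.5 = 8.2.
- Effect: "Statistical Power to detect a Hazards Ratio of 0.8". "All power calculations are for 2-tailed testing and assume" alpha = 0.05.
- Horizon: 15 years (Statistical power). Parent trial: 1,791 enrolled, median follow-up 5.6 years. Main Cohort: 1031.

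**The plan's own figure.** The plan states no absolute risk. Its nearest figure is the updated 15-year power of 86.3%. With constant hazards and no competing death:
- Events to 5.6 years: 1791 × (1 - exp(-0.0519 × 5.6)) ≈ 452.
- Events from 5.6 to 15 years: 1031 × exp(-0.0519 × 5.6) × (1 - exp(-0.0519 × 9.4)) ≈ 298.
- Total ≈ 749. Schoenfeld power = Φ(√(749/4) × |ln 0.8| - 1.96) = 0.863, which reproduces the plan.
- With non-CV death at 8.2 per 1000: 729 events and power 0.854. Competing death barely affects power.

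**Formulas.** With event hazard l, competing hazard m and time T:
- Life-table risk = 1 - exp(-lT).
- Cumulative incidence = l/(l+m) × (1 - exp(-(l+m)T)).

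**Standard arm, 15 years.** l = 0.0519, m = 0.0082.
- Life table: 1 - exp(-0.7785) = 54.1%.
- Cumulative incidence: 0.0519/0.0601 × (1 - exp(-0.9015)) = 51.3%.

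**Intensive arm, 15 years.** l = 0.8 × 0.0519 = 0.04152, same m.
- Life table: 1 - exp(-0.6228) = 46.4%.
- Cumulative incidence: 0.04152/0.04972 × (1 - exp(-0.7458)) = 43.9%.

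**By horizon at Table 2 rates** (RD = risk difference in points):

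| Years | Life table, standard arm | Cumulative incidence, standard arm | Excess | RD, life table | RD, cumulative incidence |
|---|---|---|---|---|---|
| 6 | 26.8% | 26.1% | 0.6 | 4.7 | 4.6 |
| 10 | 40.5% | 39.0% | 1.5 | 6.5 | 6.3 |
| 15 | 54.1% | 51.3% | 2.8 | 7.7 | 7.4 |

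**By non-CV death rate at 15 years.** Rates of 20 and above are assumed, because the documents give none for the ageing cohort. The life-table values stay at 54.1% and 46.4%.

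| Non-CV deaths per 1000 | Cumulative incidence, standard | Cumulative incidence, intensive | Excess, standard arm | RD |
|---|---|---|---|---|
| 8.2 | 51.3% | 43.9% | 2.8 | 7.4 |
| 20 | 47.6% | 40.7% | 6.5 | 7.0 |
| 30 | 44.8% | 38.2% | 9.3 | 6.6 |
| 40 | 42.2% | 35.9% | 11.8 | 6.3 |

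**If non-CV death differs by arm** (standard arm at 8.2 per 1000). The life-table RD stays at 7.7 points. At a non-CV death hazard ratio (intensive to standard) of 0.8 the cumulative incidence RD is 6.9; at 1.22 it is 7.9. The two RDs are equal at a ratio of about 1.14, or 1.16 if the standard-arm rate is 30 per 1000. Above that point the life table understates the difference.

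**CV mortality, 15 years, standard arm.** l = 0.0055, m = 0.0082: 7.9% by life table against 7.5%; RD 1.53 against 1.44 points.

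**The case against.** The strongest reply is that nothing the plan commits to is wrong. The target effect is a hazard ratio, the test is the log-rank test, and that test is valid for the cause-specific hazard when non-CV death is censored. No section promises an absolute risk, a risk difference or a number needed to treat. The censoring itself is inferred, since the text defers to parent-trial methods that these documents do not set out. Keeping those methods also aids comparison with the parent trial and the published mid-point analysis. All of this stands. It limits the point to the curves and to anything read from them, and it makes an unstated rule part of the problem.

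Three stronger readings are tempting, and the documents do not support them.
- **That the treatment benefit is overstated.** At Table 2 rates the shift is 0.3 points, or a number needed to treat of 12.9 against 13.5, and its direction depends on non-CV death by arm.
- **That every death competes.** CV death is an event in the primary endpoint, and total mortality has no competitor.
- **That the microvascular bias can be read from Table 2.** Setting 31.4 per 1000 against total mortality of 13.7 gives 37.6% against 34.2%. But the Table 2 footnote includes severe visual impairment and ischemic amputation, whereas the Major secondary end-points list has end-stage renal disease or non-ischemic amputation. The documents give no rate for that endpoint. At assumed rates of 2 to 10 per 1000 the gap would be 0.3 to 1.3 points.

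**Conclusion.** The point holds for absolute risk, conditional on non-CV death being censored. On the plan's own rates, the 15-year life-table risk is 2.8 points too high in the standard arm and 2.5 points too high in the intensive arm (46.4% against 43.9%). The excess in the standard arm would be about 6.5 to 12 points if non-CV death averaged an assumed 20 to 40 per 1000. The between-arm difference is only slightly misstated at Table 2 rates, and could be misstated in either direction if non-CV death differs by arm. A reader might infer that the primary p-value or the power is compromised; neither is.

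The figures assume constant hazards, the same non-CV death rate before a first CV event as overall, equal non-CV death in the arms unless stated, and 51.9 per 1000 as the standard-arm rate. Taking 51.9 as the average of the two arms gives 57.9% against 55.0% in the standard arm and an RD of 7.95 against 7.63, so the conclusion does not depend on that choice.

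This is an inexpensive improvement to the reporting, worth making before the final analysis, and not a flaw in the primary test.

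**What to change.** - Keep the log-rank test as the primary comparison, and state that non-CV death is censored for it.
- Present Aalen-Johansen cumulative incidence by arm. Non-CV death competes for the primary endpoint, CV mortality and the micro- or macrovascular composite. All death competes for microvascular events where they are analysed as time to event under the Update.
- Base any absolute risk, risk difference or number needed to treat on these curves, and show the competing-death curve by arm beside them.
- State how deaths of undetermined cause are classed, with a sensitivity analysis under the alternative classification.

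Total mortality needs no change.

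The cost is some SAP wording and a modest extra analysis using cause-of-death data already being collected; the primary test and its alpha are untouched. Reported absolute risks will be somewhat lower, and the curves will differ in form from the parent trial's. Life-table curves can be kept as a supplement for comparability.
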